4.1.2.1 Rapid Induction

The flow of activities for participants in the rapid induction arm is provided in Figure 3.

After completing the pre-TM buprenorphine assessments, participants will then be administered 4 mg of TM buprenorphine.

After a minimum of 1 hour has elapsed since the 4-mg dose of TM buprenorphine was administered, the participant will be re-assessed for withdrawal symptoms (COWS) and tolerability (AEs). Participants must meet **all** of the following criteria to receive RBP-6000 using rapid induction:

- 1. The participant does not display any allergic/hypersensitivity reaction to TM buprenorphine.
- 2. Based on the Investigator's judgment, the participant did not experience precipitated withdrawal symptoms from the most recent TM buprenorphine administration that would prevent RBP-6000 administration.
- 3. Based on the Investigator's judgment, the participant is not sedated (i.e., participant cannot be easily aroused by external stimuli).

After receiving TM buprenorphine, if the participant is sedated or has precipitated withdrawal symptoms that would prevent RBP-6000 administration, in the opinion of the Investigator, the participant may either remain in the clinic to repeat the 4 mg TM buprenorphine later that same day or may return to the site and repeat the induction within 30 days of informed consent.

If the participant is eligible for dosing with RBP-6000, pre–RBP-6000 assessments will be conducted including, but not limited to, vital signs, will be collected. If the participant is eligible, 300 mg RBP-6000 may be administered SC and the visit will be considered Day 1.

Participants will be asked to remain in the clinic for at least 4 hours post-RBP-6000. A COWS assessment will be completed at 1, 2 and 4 hours and an injection site evaluation will be completed at 1 and 2 hours post–RBP-6000.

[figure not shown]
All AEs and concomitant medications should be recorded. If the participant experiences withdrawal symptoms post RBP-6000 on Day 1, the participant may be treated symptomatically (SAMHSA TIP 63 2020; see Section 9.13 for treatment of withdrawal symptoms). Also, following the first injection of 300 mg RBP 6000, TM buprenorphine in increments of 2 to 4 mg up to a maximum dose of 12 mg (inclusive of pre–RBP-6000 TM buprenorphine) may be administered on Day 1 at the discretion of the Investigator to alleviate withdrawal symptoms while on site.

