4.1.2.2 Standard of Care (SoC) Induction

After completing the pre-TM buprenorphine assessments, participants should then be inducted per SoC according to the applicable TM buprenorphine product labelling

information, that is, a participant should be dose-adjusted onto TM buprenorphine for a minimum of 7 days.

On the first induction day, participants will be asked to remain in the clinic for at least 5 hours after the first TM buprenorphine dose, completing COWS assessments at 1, 2, 3 and 5 hours post TM buprenorphine. All AEs and concomitant medications should be recorded. If the participant experiences exacerbated withdrawal symptoms at any time, he/she may be treated symptomatically.

Prior to the participant leaving the site, the Investigator will be asked to assess the following:

• Did the participant experience precipitated withdrawal after TM buprenorphine, and if so, which AEs were associated with the event?

Any doses of TM buprenorphine administered at the site, dispensed to the participant and taken by the participant outside of the clinic should be recorded. For reconciliation, participants will be asked to return any doses not taken as well as the empty packaging for all doses taken. The Investigator may ask the participant to return for dose adjustment as many times as necessary per SoC, recording any AEs and concomitant medications at each visit.

Participants must meet **all** of the following criteria to receive RBP-6000 using SoC induction:

- 1. The participant has been dose-adjusted onto TM buprenorphine for a minimum of 7 days and, based on the Investigator's judgment, appears eligible for dosing with RBP-6000.
- 2. The participant does not display any allergic/hypersensitivity reaction to TM buprenorphine.
- 3. Based on the Investigator's judgment, the participant did not experience precipitated withdrawal from the most recent TM buprenorphine administration that would prevent RBP-6000 administration.
- 4. Based on the Investigator's judgment, the participant is not sedated (i.e., participant cannot be easily aroused by external stimuli).
- 5. The participant has a negative pregnancy test (if female and of childbearing potential).

If a female participant has a positive pregnancy test, she will be discontinued from the study and will not proceed with subsequent assessments.

assessments will be conducted including (but not limited to) TLFB, COWS,

12-lead ECG, vital signs,

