5.3 Exclusion Criteria

A participant will not be eligible for inclusion in this study if **any** of the following criteria apply:

- 1. Has current diagnosis, other than OUD, requiring chronic opioid treatment.
- 2. Has concurrent primary substance use disorder, as defined by DSM-5 criteria, other than opioid, tobacco, cannabis or alcohol use disorders.
- 3. Meets DSM-5 criteria for severe alcohol use disorder.
- 4. Has had significant traumatic injury or major surgical procedure (as defined by the Investigator) within 30 days prior to the first dose of RBP-6000 or still recovering from prior such injury or surgery.
- 5. Has congenital long QT syndrome, history of prolonged QT in the 3 months prior to Screening, or history of medications or other factors that are at risk for Torsades de Pointes.
- 6. Has abdominal area unsuitable for SC injections (e.g., nodules, scarring, lesions, excessive pigment).
- 7. Has history of suicidal ideation within 30 days prior to informed consent or history of a suicide attempt in the 6 months prior to informed consent.
- 8. Has uncontrolled intercurrent illness including, but not limited to, a medical or psychiatric illness/social situation that would limit compliance with study requirements or compromise the ability of the participant to provide written informed consent.

- 9. Has any other active medical condition, organ disease or concurrent medication or treatment that may either compromise participant safety or interfere with study endpoints.
- 10. Has total bilirubin ≥1.5 × upper limit of normal (ULN) (with direct bilirubin >1.3 mg/dL), ALT ≥3 × ULN, AST ≥3 × ULN, serum creatinine >2 × ULN, or international normalised ratio (INR) >1.5 × ULN at Screening.
- 11. Has known allergy or hypersensitivity to buprenorphine or any component of the ATRIGEL Delivery System.
- 12. Is undergoing concurrent or has had prior treatment with any long -acting form of a buprenorphine-containing product in the past 2 years, or if >2 years has a positive UDS for buprenorphine at screening; treatment with oral buprenorphine, oral naltrexone or methadone products within 14 days prior to consent; or treatment with depot naltrexone within the 3 months prior to consent.
- 13. Is undergoing concurrent treatment with another investigational agent or enrolment in another clinical study (except for an observational study) or treatment with another investigational agent within 30 days prior to Screening.

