3. SUB-STUDY ENDPOINTS

The primary endpoint of this sub-study is treatment retention at Injection 2 defined as the proportion of participants receiving Injection 2 at the Week 2 visit among those who received at least 1 dose of TM buprenorphine for induction and did not demonstrate idiosyncratic response to the first dose of TM buprenorphine. Participants who discontinue treatment due to not meeting Inclusion/Exclusion criteria will be excluded.

The secondary endpoints of this sub-study are the following:

- time to treatment discontinuation from the first dose of TM buprenorphine used for induction during the Open-label Treatment Period (OLTP) defined as the number of days from the first dose of TM buprenorphine until the last scheduled visit observed during the OLTP. Participants receiving the third RBP-6000 injection (i.e., the first randomised injection) will be censored administratively at the end of the OLTP; otherwise participants will be viewed as having discontinued treatment at their last scheduled visit observed during the OLTP. Participants discontinued due to idiosyncratic response to the first dose of TM buprenorphine or not met meeting Inclusion/Exclusion criteria will not be included.
- adverse events up to Injection 2, and between Injections 2 and 3

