**Table 5. Populations for Analysis** 

Population	Description
Screened	All participants who sign the informed consent form.
Sub-study Randomised Population (SRP)	The SRP will comprise all participants who give informed consent and are randomised to sub-study treatment. The participants will be analysed corresponding to the induction arm to which they were randomised (ie, planned arm).
Sub-study Full Analysis Set (SFAS)	The SFAS will comprise all participants who are randomised to sub-study treatment and receive the first dose of TM BUP and do not demonstrate idiosyncratic response to the first dose of TM BUP (ie, allergic / hypersensitivity reaction to TM BUP as recorded on the electronic case report form [eCRF] disposition). The participants will be analysed corresponding to the induction arm they received ("as treated", ie, actual arm), given that logistically it is highly unlikely for them to receive the induction arm that they were not randomised to since the randomised arm triggers eCRF forms corresponding to the schedule of events for that arm. Participants who were randomised and inducted with neither RI or SoC (which is a key protocol deviation) will be excluded from the SFAS. The SFAS will serve as the primary population for the analysis in this sub-study.
Evaluable Population for Treatment Retention/Discontinuation a	For analysis pertaining to treatment retention and time-to-treatment discontinuation, the SFAS participants who discontinue treatment within the sub-study due to not meeting Inclusion/Exclusion criteria will be also excluded. The participants will be analysed corresponding to the induction arm they received ("as treated", ie, actual arm).

a Note that this population is described in the protocol but was not given a distinct population name. It is named in this statistical analysis plan for ease of reference and clarity in estimand and analysis specifications.

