#### 5.1.4 Open-label Induction Sub-study Period

The treatment period for the OLIS begins when the first TM BUP dose is given and ends immediately prior to a participant receiving double-blind RBP-6000 Injection 3. Note that predose assessments for Injection 3 are considered part of the OLIS. See Figure 1 for the OLIS schematic.

For the RI arm, the Induction Day 1 Visit of the most recent induction attempt and the Week 1 Day 1 Visit for the first RBP-6000 injection occur on the same calendar day. In the protocol, this day is the "Day 1" of the RI arm: the RI participants receive their first RBP-6000 injection about 1 hour post TM BUP and then remain on site about 4 hours post injection. The investigator-evaluated PWs occurring within the 1-hour window post TM BUP under Induction Day 1 Visit and those occurring within the 4-hour window post RBP-6000 injection under Week 1 Day 1 Visit are recorded on "Day 1" of the RI arm.

[figure not shown]
For the SoC arm, the Week 1 Day 1 Visit for the first RBP-6000 injection occurs about 7 to 14 days after the Induction Day 1 Visit. At the Induction Day 1 Visit (of the most recent induction attempt), the SoC participants remain on site about 5 hours after the first TM BUP, to serve as the control period for the 5-hour on-site duration post TM BUP on "Day 1" of the RI arm; at Week 1 Day 1 Visit, the SoC participants remain on site about 4 hours post RBP-6000 injection at Week 1 Day 1 Visit, to serve as the control period for the 4-hr on-site duration post injection on "Day 1" of the RI arm.

Therefore, the Induction Day 1 Visit or the Week 1 Day 1 Visit will be used to refer to the "Day 1" of the RI arm, depending on which visit of the SoC arm is to be compared.

Handling of multiple Induction Check-in Days/repeat attempts at induction are described in the analysis sections for the individual endpoints. Example scenarios that may result in multiple Induction Check-in Days/repeated attempts at induction are the following:

- PW from TM BUP that would prevent RBP-6000 administration
- Participant must leave before the in-clinic assessments on an Induction Day Visit are completed

Figure 1. Open-label Induction Sub-study Schematic

BUP=buprenorphine; min=minimum; SoC=standard of care; TM=transmucosal

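### The sub-study's primary population drops participants stopped on eligibility grounds without requiring that the failure predate randomisation, so post-randomisation events can remove failures, mainly from the SoC arm

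*SAP*

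**What the plan says.** The primary endpoint is analysed in the Evaluable Population for Treatment Retention/Discontinuation (SAP 5.3). SAP Table 5 builds that population from the SFAS and adds that "the SFAS participants who discontinue treatment within the sub-study due to not meeting Inclusion/Exclusion criteria will be also excluded". Protocol Appendix 22.9, section 3, has the same rule: "Participants who discontinue treatment due to not meeting Inclusion/Exclusion criteria will be excluded". Section 8.4.2 of that appendix repeats it. The sub-study period runs from the first TM buprenorphine dose to just before Injection 3 (SAP 5.1.4), so the removal window lies wholly after randomisation.

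Exclusion 4 (Protocol 5.3) concerns significant trauma or major surgery "within 30 days prior to the first dose of RBP-6000 or still recovering from prior such injury or surgery". Its clock is neither consent nor randomisation.

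The arms reach that dose at different times. In rapid induction, "the RI participants receive their first RBP-6000 injection about 1 hour post TM BUP". In SoC, a condition for the injection is that "The participant has been dose-adjusted onto TM buprenorphine for a minimum of 7 days", and SAP 5.1.4 expects that "the first RBP-6000 injection occurs about 7 to 14 days after the Induction Day 1 Visit".

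A participant who stays in the population but does not receive Injection 2, or Injection 3 after a missed Injection 2, is scored *No* (SAP Table 6). The visible sensitivity analysis (SAP 5.3.3) changes the arm label from actual to planned. SAP Table 2 keeps its population the same as the primary.

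**The concern.** Removing randomised people for ineligibility is neutral when the failure existed before randomisation and is looked for in the same way in both arms. The rule asks for neither. Exclusion 4 can become true after randomisation. It stays open for at least a week in SoC, and normally for about an hour in rapid induction.

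Take the same injury a few days after randomisation. A SoC participant has not yet been injected, can be recorded as failing exclusion 4, and can then leave both numerator and denominator. A rapid-induction participant has already been injected, cannot newly fail exclusion 4, and counts as not retained if he or she stops.

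Pregnancy testing adds a second, smaller difference. SoC has a further test before the first RBP-6000 dose (Protocol 4.1.2.2), which the rapid-induction list after TM buprenorphine (4.1.2.1) does not have. Non-pregnancy is part of inclusion 9.

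What is at stake is whether the non-inferiority comparison is between the groups as randomised. The sub-study is open-label, so the stop reason is recorded with the arm known.

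**Working it through.** **Inputs.** 489 participants at 2:1, so 326 rapid and 163 SoC; 70% retention in both arms; looks at 120, 240 and 489; 10-point margin; stated power 77.2% (SAP 3). Beta(1,1) priors and success at a posterior probability of 96% or more (SAP 5.3.2). Overall one-sided type I error stated as 0.0941 at 0.70 versus 0.60 (SAP Table 3).

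**Reproducing the plan.** I applied the rule P(p_R − p_SoC > −0.10) ≥ 0.96 at looks of 80/40, 160/80 and 326/163, with 400,000 simulated trials per scenario. Power is about 77.2% (stated 77.2%) and type I error about 0.093 (stated 0.0941). The plan's figures stand. Exact enumeration agrees with the simulated values below to within 0.2 points of power and 0.001 of type I error.

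**Effect per participant.** 0.70 × 163 ≈ 114 retained. Removing SoC failures gives:
- none: 114/163 = 69.9%
- one: 114/162 = 70.4%
- three: 114/160 = 71.3%
- five: 114/158 = 72.2%

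Each removal adds about 0.43 points to SoC retention, against a 10-point margin.

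**Effect on the design.** Let e be the share of an arm removed, all of them failures. That arm's rate becomes p/(1 − e) and its size n(1 − e) at every look. The documents give no e, so a range is shown. Power is at 0.70/0.70 and type I error at SoC 0.70, rapid 0.60.

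| Removed | Participants, about | Power | Type I error |
|---|---|---|---|
| none | 0 | 77.2% | 0.093 |
| 0.5% of SoC | 1 of 163 | 74.9% | 0.083 |
| 1% of SoC | 2 of 163 | 72.3% | 0.074 |
| 2% of SoC | 3 of 163 | 67.1% | 0.060 |
| 5% of SoC | 8 of 163 | 48.8% | 0.027 |
| 2% of both arms | 3 and 7 | 77.9% | 0.088 |

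**How plausible are such counts?** Two SoC removals through exclusion 4 alone are 2/163 = 1.2% over 7 to 14 days. That is 0.012 × 365/14 ≈ 0.3 to 0.012 × 365/7 ≈ 0.6 events per person-year. Five removals need about 0.8 to 1.6. The lower rows of the table are therefore illustrations, not forecasts.

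**The other direction.** If the open-ended rule removed rapid-arm failures only, 0.5% (about 2 of 326) gives type I error of about 0.103 and 1% (about 3 of 326) about 0.11, against the stated ceiling of 0.10. This is an assumption about the rule in general. Exclusion 4 does not supply such a route once a rapid-arm participant has been injected.

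**The case against.** The strongest reply is that nothing says a run-in injury is coded this way. Randomisation requires that no exclusion applies (Protocol 9.4.1), the inclusion/exclusion row appears only at Screening (Appendix 22.1), and the SoC injection criteria do not name exclusion 4. Such a stop could equally be recorded as an adverse event or as investigator discretion. The text of Protocol 6.7.1 on withdrawal from treatment is not visible and may govern stop reasons. This stands, and it limits the point to *can remove*. It does not close the route, because Protocol 9.7.2 has eligibility confirmed before RBP-6000 is dispensed and exclusion 4 is dated to that dose.

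Rapid induction is also not immune. A participant "may return to the site and repeat the induction within 30 days of informed consent", which opens a gap of days there too. The Week 2 pregnancy test before Injection 2 (Appendix 22.4) applies to both arms, so SoC has one extra test, not the only one.

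A reader might infer that the local and central laboratory arrangement (Protocol 4.1.1) is a further route. That is weak: the central sample supplies a baseline value, liver results are required before TM buprenorphine (Appendix 22.1), and the sample predates randomisation.

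Part of the remedy already exists. SAP 5.2.2 tabulates discontinuation reasons, population counts and failed entry criteria. Those tables would show removals if split by arm, but they do not replace the re-analysis.

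**Conclusion.** The population rule has a real gap. It allows post-randomisation events to take participants out of the primary analysis, and the dating of exclusion 4 makes this more likely in SoC. No visible planned analysis puts them back.

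The size depends on an unknown count that is probably small. One SoC removal costs about 2 points of power, and three cost about 10, assuming 70% true retention in both arms, all removed participants being failures, and none removed from rapid induction.

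A reader might infer that the rule makes a false declaration of non-inferiority more likely. Through exclusion 4 it does the opposite: it raises SoC retention and lowers type I error. Error control would be at risk only if rapid-arm failures were removed selectively by some other route, and the documents describe none. The case for change is that the present wording leaves both directions open in an open-label comparison, and closing it is cheap.

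**What to change.** 1. In SAP Table 5 and Protocol Appendix 22.9 (sections 3 and 8.4.2), limit the exclusion to criteria shown, by data dated on or before randomisation, to have been failed at randomisation. Make that judgement without knowledge of arm or outcome.
2. Score every other eligibility discontinuation before Injection 2 as *No* under SAP Table 6.
3. Add one sensitivity run of the beta-binomial model with all eligibility removals kept in and scored *No*.
4. Report eligibility removals by arm within the disposition tables already planned in SAP 5.2.2.
5. The sponsor should reconcile the anchor date of exclusion 4 (Protocol 5.3) with the Screening-only eligibility check (Appendix 22.1) and the confirmation before RBP-6000 (9.7.2). No clinical rule is proposed here.

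The cost is a few sentences and one extra model run. The downside is that a few truly unsuitable participants would count as not retained.

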#### **5 STATISTICAL ANALYSES**

#### 5.1 General Considerations

#### 5.1.1 Analysis Conduct

The interim and final analyses for the sub-study will be performed using SAS® Version 9.4 or SAS EG Version 7.1 (SAS Institute Inc., Cary, North Carolina, United States of America) on a Unix operating system. The interim analyses will be performed using a snapshot extraction of the relevant electronic case report form (eCRF) and external data as of a specified cut-off date. The interim analyses cut-off dates will be determined based on the interim analysis sample size and population requirements described in Section 5.8. The final analysis also will be performed using a snapshot extraction of the relevant eCRF and external data as of a specified cut-off date. The final analysis cut-off date will be determined after screening has closed for the study and all participants have completed the OLIS. The final analysis will be performed irrespective of the number of IAs.

If NI is declared at the first or second IA and the results of the IA are submitted to regulatory authorities, then all of the endpoints (primary, secondary, ), participant disposition, baseline demographic characteristics, and disease history will be analysed for inclusion in the interim CSR.

Adverse events (AE) and medical/surgical history will be coded using the Medical Dictionary for Regulatory Activities (MedDRA) and the concomitant medications will be coded using World Health Organization Drug Dictionary. Dictionary versions and additional details of the coding process are described in the Data Management Plan.

#### 5.1.2 Analysis Conventions

For participants who re-screen, only the most recent screening attempt will be included.

Continuous variables will be summarised using descriptive statistics such as mean, standard deviation [SD], median, minimum, and maximum. In addition, geometric mean and coefficient of variation will also be summarised for BUP plasma concentration. Categorical variables will be reported as frequency counts (including number missing) and the percentage of participants in corresponding categories.

Individual participant data will be presented by participant in data listings for the Screened Population unless otherwise specified. Data listings will include all data collected from the initial Screening Visit to Injection 3 Visit (Week 6 Day 36 Visit), including unscheduled and end-of-study visits occurring before reaching Injection 3 (Week 6 Day 36 Visit).

Tables and figures presenting summary data will include scheduled timepoints/visits and assessments only. Figures of individual participant data will include all timepoints/visits, scheduled and unscheduled. Timepoints/visits will be presented chronologically.

Observed data are used for analysis, unless handling of missing data is described otherwise within the analysis description or in Section 6.4.

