8 DESCRIPTION OF STUDY PROCEDURES

Study assessments and procedures, including the timing of assessments, are summarised in tables accessible through Table 2.

A signed written ICF must be obtained from the participant before any study assessments or procedures may be performed. At Screening, if an assessment or procedure has already been performed as part of routine SoC and was completed within the protocol-specific Screening window, the assessment or procedure does not need to be repeated, unless clinically indicated and must be clearly documented in the source that the assessment was performed as part of SoC. All assessments and procedures may be performed more frequently, if clinically indicated, and will be recorded in the eCRF as unscheduled visits.

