#### 5.6.5 Electrocardiograms

At each nominal scheduled visit using the most recent induction attempt, electrocardiogram (ECG) numeric variables (heart rate, PR interval, QRS duration, QT Interval, and QT interval corrected using Fridericia's method, QTcF, change from screening for QTcF) will be summarised overall, by induction arm, and within individual randomisation strata for the SFAS. In addition, the number and percentage of participants with QTcF >500 msec and with the QTcF change from Screening to each nominal scheduled visit >60 msec will be summarized overall, by induction arm, and within individual randomisation strata for the SFAS.

The investigator's assessment of ECG results (normal/abnormal and if abnormal, clinically significant yes/no) will be listed.

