### 5.6.6.1 Factors of Upper Limit of Normal

The number and percentage of participants meeting liver function test criteria for ALT, AST, and total bilirubin during the timeframe after the first dose of TM BUP up to and including Week 6 will be summarised overall, by induction arm, and within individual randomisation strata. For each lab parameter, the participant will be counted only once according to their worst case (highest) result during the timeframe. The criteria are factors of upper limit of normal (ULN), as follows:

- a. ALT (>3×ULN)
  - >=8×ULN
  - >=5×ULN to <8×ULN

  - >3×ULN to <5×ULN

- b. AST (>3×ULN)
  - >=8×ULN
  - >=5×ULN to <8×ULN

  - >3×ULN to <5×ULN

- c. Total Bilirubin (>2×ULN)
  - >=5×ULN

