#### 5.6.6.2 LFT values

At each nominal scheduled visit using the most recent induction attempt, LFT results and the change in LFT result from screening will be summarised overall, by induction arm, and within individual randomisation strata.

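### The sub-study SAP limits all summary tables to scheduled assessments, so its QTcF threshold counts omit unscheduled ECGs and its worst-case liver table rests on conflicting rules

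*SAP*

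**What the plan says.** SAP 5.1.2 governs all summary output: "Tables and figures presenting summary data will include scheduled timepoints/visits and assessments only". Unscheduled results are given two other places. The data listings include them up to Injection 3, and for graphs of single participants the rule is: "Figures of individual participant data will include all timepoints/visits, scheduled and unscheduled".

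SAP 5.6.5 summarises ECG variables by nominal scheduled visit, using the most recent induction attempt, and then adds "the number and percentage of participants with QTcF >500 msec and with the QTcF change from Screening to each nominal scheduled visit >60 msec".

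SAP 5.6.6.1 works differently. It tabulates ALT, AST and total bilirubin against multiples of the upper limit of normal "during the timeframe after the first dose of TM BUP up to and including Week 6", and "the participant will be counted only once according to their worst case (highest) result during the timeframe". It closes by listing the liver data of participants who meet the criteria. The next subsection, 5.6.6.2, is visit-based: "At each nominal scheduled visit using the most recent induction attempt, LFT results and the change in LFT result from screening".

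The protocol foresees extra testing. Section 8 states: "All assessments and procedures may be performed more frequently, if clinically indicated, and will be recorded in the eCRF as unscheduled visits". Section 8.7.5 leaves additional 12-lead ECGs to the investigator's discretion.

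**The concern.** A threshold count answers a simple question: how many participants ever crossed the limit? A rule that drops unscheduled tests answers a narrower one: how many crossed it at a planned visit? An ECG or liver panel taken because something looked wrong is, by the protocol's own terms, an unscheduled assessment, so it is the kind of result the rule removes.

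For QTcF, a value above 500 msec seen only on an extra ECG would be missing from the table. For liver tests, two competent programmers could build different tables from the same SAP. One of those tables could show fewer participants above a limit than the accompanying listing. At stake is the completeness of the objective hepatic and cardiac counts in an open-label comparison of rapid and standard-of-care induction.

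**Working it through.** The SAP gives no figure to reproduce, and the point depends on no sample size, error rate or power. The check sets the rules side by side and then works out the direction of any error.

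**Step 1: the rules**

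| Place | Which results count | Limited to scheduled visits? |
|---|---|---|
| SAP 5.1.2, summary tables and figures | Scheduled only | Yes, with no exception clause |
| SAP 5.1.2, listings and individual figures | Scheduled and unscheduled | No |
| SAP 5.6.5, QTcF | By nominal visit, most recent induction attempt | Yes |
| SAP 5.6.6.1, worst-case liver table | Highest result in a time window | Not stated |
| SAP 5.6.6.2, liver values | By nominal visit | Yes |

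Elsewhere in 5.1.2, the rule on the listing population and the rule on missing data each allow for a different specification. The scheduled-only sentence has no such allowance.

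**Step 2: QTcF.** The count of changes above 60 msec names the nominal scheduled visit directly. The count above 500 msec takes its visit frame from the preceding sentence of 5.6.5, and nothing there overrides 5.1.2. Both routes lead to scheduled ECGs only. No count over the whole period is defined.

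**Step 3: liver tests.** Section 5.6.6.1 sets a window and a maximum, which points to every result in the window. Section 5.1.2, taken literally, restricts the same table to scheduled results. Neither section yields to the other. The listing follows the listing rule, which admits unscheduled visits. Under the literal reading of 5.1.2, a participant can therefore appear in the listing and not in the table.

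**Step 4: direction.** For one participant, let S be the scheduled results in the period, U the unscheduled results and L the limit.

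- Scheduled-only count: the participant is counted if max(S) > L.
- Any-time count: the participant is counted if max(S ∪ U) > L.
- Because S is contained in S ∪ U, max(S) ≤ max(S ∪ U). Summed over participants, the scheduled-only count is at most the any-time count.
- The shortfall is the number of participants with max(S) ≤ L < max(U).

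This holds for any count above a limit. Within the liver bands, a scheduled-only rule can also misplace people. A participant whose scheduled ALT peak lies between 3 and 5 times the upper limit, but whose unscheduled peak is 8 times or more, falls in the lowest band instead of the highest. The effect on the difference between arms has no fixed sign, since it depends on where the missed results fall.

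**Step 5: size.** The shortfall needs the rate of unscheduled testing and the share of exceedances seen only there. The documents give neither, so no number is offered.

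**The case against.** The strongest reply concerns the liver table. The authors wrote a visit limit into 5.6.3, 5.6.5 and 5.6.6.2 but not into 5.6.6.1, and a specific rule normally prevails over a general convention. The version history fits this reading: sections 5.6.3 to 5.6.7 came in with SAP version 3.0, whose only logged change to 5.1.2 concerned re-screened participants, so the scheduled-only sentence probably predates the liver and ECG tables. This stands to the extent that exclusion from the liver table is not certain. A reader might infer that the table definitely leaves out unscheduled tests; the text shows only an unresolved conflict.

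The second reply is that important unscheduled findings reach tables by another route. Clinically significant laboratory values and ECGs become adverse events (protocol 8.7.3.2 and 8.7.5). ALT or AST above 3 times the upper limit with bilirubin above 2 times is serious by definition (protocol 11.1) and has its own row in the SAP. Treatment-emergent events are assigned by onset date, not by visit. This also stands, so it would be wrong to infer that such findings survive only in listings. It does not close the gap: that route depends largely on the investigator's judgement of clinical significance, and the dedicated serious-event row covers only the combined liver criterion. Threshold counts are useful because they need no such judgement.

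Third, the protocol's secondary endpoints for safety are the adverse event proportions up to Injection 2 and between Injections 2 and 3. The ECG and liver summaries are additions recorded in SAP 6.2. The secondary endpoints are therefore untouched.

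Finally, the SAP places detailed output specifications in a separate document, which may settle some of this but was not available.

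**Conclusion.** The point holds in two parts. As written, the QTcF counts above 500 msec and for a rise above 60 msec exclude unscheduled ECGs, and no any-time count replaces them. The worst-case liver table is governed by two rules that disagree, and the disagreement can separate the table from its listing.

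The number above a limit could be understated and cannot be overstated. It is unchanged if no participant crosses a limit only on an unscheduled test.

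Three further inferences are not supported. The documents do not say that peak values are mostly found on unscheduled tests, only that clinically indicated extra tests are recorded that way. They give no basis for a numerical undercount. They do not show that early-termination results are excluded: that visit has its own column in protocol Appendix 22.6, with ECG and serum chemistry, and the SAP does not say whether it counts as scheduled.

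The conclusion applies to the sub-study SAP; no main-study SAP is among the documents. It is worth correcting before the tables are programmed, but it does not threaten the primary analysis or the AE-based secondary endpoints.

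**What to change.** Make three edits to the SAP.

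1. In 5.1.2, confine the scheduled-only rule to by-visit descriptive summaries.
2. In 5.6.6.1, state that the worst-case count uses every result in its window, whether scheduled, unscheduled or from early termination. The table and the listing then draw on the same records.
3. In 5.6.5, keep the by-visit summaries and add any-time counts of QTcF above 500 msec and of change from Screening above 60 msec. These should use all ECGs after the first dose of transmucosal buprenorphine in the sub-study period, including unscheduled and early-termination ECGs.

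The cost is a few sentences and a changed record filter in programming. No new data are needed, because unscheduled results are already collected and due to be listed.
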